11.43 Response Criteria

- 11.431 All target lesions and target lymph nodes followed by CT/MRI must be measured on re-evaluation at evaluation times specified in Section 11.1. Specifically, a change in objective status to either a PR or CR cannot be done without re-measuring target lesions and target lymph nodes.

Note: Non-target lesions and non-target lymph nodes should be evaluated at each assessment, especially in the case of first response or confirmation of response. In selected circumstances, certain non-target organs may be evaluated less frequently. For example, bone scans may need to be repeated only when complete response is identified in target disease or when progression in bone is suspected.

11.432 Evaluation of Target Lesions

- Complete Response (CR): All of the following must be true:
 - a. Disappearance of all target lesions.
 - b. Each target lymph node must have reduction in short axis to <1.0 cm.
- Partial Response (PR): At least a 30% decrease in PBSD (sum of the longest diameter for all target lesions plus the sum of the short axis of all the target lymph nodes at current evaluation) taking as reference the BSD (see Section 11.41).

- Progression (PD): At least one of the following must be true:
 - a. At least one new malignant lesion, which also includes any lymph node that was normal at baseline (< 1.0 cm short axis) and increased to \geq 1.0 cm short axis during follow-up.
 - b. At least a 20% increase in PBSD (sum of the longest diameter for all target lesions plus the sum of the short axis of all the target lymph nodes at current evaluation) taking as reference the MSD (Section 11.41). In addition, the PBSD must also demonstrate an absolute increase of at least 0.5 cm from the MSD.
- Stable Disease (SD): Neither sufficient shrinkage to qualify for PR, nor sufficient increase to qualify for PD taking as reference the MSD.

11.433 Evaluation of Non-Target Lesions & Non-target Lymph Nodes

- Complete Response (CR): All of the following must be true:
 - a. Disappearance of all non-target lesions.
 - b. Each non-target lymph node must have a reduction in short axis to <1.0 cm.
- Non-CR/Non-PD: Persistence of one or more non-target lesions or non-target lymph nodes.
- Progression (PD): At least one of the following must be true:
 - a. At least one new malignant lesion, which also includes any lymph node that was normal at baseline (< 1.0 cm short axis) and increased to \geq 1.0 cm short axis during follow-up.
 - b. Unequivocal progression of existing non-target lesions and non-target lymph nodes. (NOTE: Unequivocal progression should not normally trump target lesion and target lymph node status. It must be representative of overall disease status change.)

11.44 Overall Objective Status

The overall objective status for an evaluation is determined by combining the patient's status on target lesions, target lymph nodes, non-target lesions, non-target lymph nodes, and new disease as defined in the following tables:

For Patients with Measurable Disease

Target Lesions & Target Lymph Nodes	Non-Target Lesions & Non-Target Lymph Nodes	New Sites of Disease	Overall Objective Status
CR	CR	No	CR
CR	Non-CR/Non-PD	No	PR
PR	CR Non-CR/Non-PD	No	PR
CR/PR	Not All Evaluated*	No	PR**
SD	CR Non-CR/Non-PD Not All Evaluated*	No	SD
Not all Evaluated	CR Non-CR/Non-PD Not All Evaluated*	No	Not Evaluated (NE)
PD	Unequivocal PD CR Non-CR/Non-PD Not All Evaluated*	Yes or No	PD
CR/PR/SD/PD/Not all Evaluated	Unequivocal PD	Yes or No	PD
CR/PR/SD/PD/Not all Evaluated	CR Non-CR/Non-PD Not All Evaluated*	Yes	PD

*See Section 11.431

** NOTE: This study uses the protocol RECIST v1.1 template dated 2/16/2011. For data collection and analysis purposes the objective status changed from SD to PR in the ACCRU protocol RECIST v1.1 template as of 2/16/2011 and to match RECIST v1.1 requirements.

For Patients with Non-Measurable Disease Only:

Non-Target Lesions & Non-Target Lymph Nodes	New Sites of Disease	Overall Objective Status
CR	No	CR
Non-Target Lesions & Non-Target Lymph Nodes	No	Non-CR/Non-PD
Not All Evaluated*		
Unequivocal PD		
Any		
Non-CR/Non-PD		

*See Section 11.431

11.45 Symptomatic Deterioration: Patients with global deterioration of health status requiring discontinuation of treatment without objective evidence of disease progression at that time, and not either related to study treatment or other medical conditions, should be reported as PD due to "symptomatic deterioration." Every effort should be made to document the objective progression even after discontinuation of treatment due to symptomatic deterioration. A patient is classified as having PD due to "symptomatic deterioration" if any of the following occur that are not either related to study treatment or other medical conditions:

- Weight loss >10% of body weight.
- Worsening of tumor-related symptoms.
- Decline in performance status of >1 level on ECOG scale.

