8.3 Criteria for discontinuing treatment with regorafenib

Treatment with regorafenib will be discontinued if any of the following criteria for discontinuation is met:

1. When regorafenib is considered to be ineffective
 - Radiographically confirmed disease progression.
 - Significant worsening of symptoms or physical findings (disease progression should be radiographically confirmed whenever possible).

2. When treatment with regorafenib cannot be continued
 - It is necessary to reduce the dose of regorafenib to less than dose level -2 according to the criteria for dose reduction/modification of treatment.
 - Treatment cannot be resumed within 28 days after modification of treatment due to an adverse event.
 - A 3rd episode of grade 3 hand-and-foot syndrome occurs despite symptomatic treatment and dose reduction of regorafenib.
 - Grade 4 hypertension.
 - Grade 4 or higher increase in AST/ALT, 2nd episode of grade 3 increase in AST/ALT or bilirubin > upper limit of normal x 2 and AST or ALT > upper limit of normal x 3.
 - Other grade 4 non-hematological toxicity.
 - The treating physician decides that treatment with regorafenib cannot be continued due to safety concerns.
3. Patient's request for discontinuation of treatment with regorafenib.
4. After enrollment, the patient is found to be ineligible for the study, and it is concluded that further treatment with regorafenib is detrimental to him/her.
5. Transfer to another institution for any reason during treatment with regorafenib.

8.4 Combination therapy of Anti-EGFR therapy (cetuximab (Cmab) OR panitumumab (Pmab)) and irinotecan

Treatment with cetuximab/panitumumab or irinotecan will be started if it is confirmed that all criteria for treatment are met prior to treatment initiation. If all criteria for starting treatment with Cmab/Pmab are met, but any of the criteria for starting treatment with irinotecan is not met, only Cmab/Pmab can be administered. If the case is reversed, however, irinotecan should not be administered alone (without Cmab/Pmab).

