8.44 Criteria for discontinuing treatment including Cmab or Pmab

Treatment with Cmab/Pmab plus irinotecan or Cmab/Pmab alone will be discontinued if any of the criteria for discontinuation listed below is met. When treatment with irinotecan is discontinued due to an irinotecan-related adverse event, treatment with Cmab/Pmab alone will be continued if none of the following criteria are met:

1. When treatment including Cmab/Pmab is considered to be ineffective
 - Radiographically confirmed disease progression per RECIST 1.1.
 - Significant worsening of symptoms or physical findings (disease progression should be radiographically confirmed wherever possible).
2. When treatment with Cmab/Pmab cannot be continued
 - It is necessary to reduce the dose of Cmab/Pmab to less than dose level -3 according to the criteria for dose reduction/modification of treatment.
 - Treatment cannot be resumed within 28 days after modification of treatment due to an adverse event.
 - The 3rd episode of grade 3 skin toxicity occurs despite symptomatic treatment and dose reduction of Cmab/Pmab.
 - Grade 3 or higher infusion-related reaction related to Cmab/Pmab.
 - Grade 4 non-hematological toxicity.
 - The treating physician concludes that treatment with Cmab/Pmab cannot be continued due to safety concerns.
3. Patient's request for discontinuation of treatment with Cmab/Pmab.
4. After entry, the patient is found to be ineligible for the study, and it is concluded that further treatment including Cmab/Pmab is detrimental to him/her.
5. Transfer to another hospital for any reason during treatment including Cmab/Pmab.

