11.0 Treatment Evaluation Using RECIST Guideline

NOTE: This study uses protocol RECIST v1.1 template dated 2/16/2011. See the footnote for the table regarding measurable disease in Section 11.44, as it pertains to data collection and analysis.

Response and progression will be evaluated in this study using the new international criteria proposed by the revised Response Evaluation Criteria in Solid Tumors (RECIST) guidelines (version 1.1)³³. Changes in the largest diameter (unidimensional measurement) of the tumor lesions and the short axis measurements in the case of lymph nodes are used in the RECIST guideline.

11.1 Schedule of Evaluations: For the purposes of this study, patients should be reevaluated every 8 weeks.

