16.32 Secondary Endpoints

16.321 First Progression-Free Survival (PFS1)

Progression-free survival one (PFS1) is defined as the time interval between randomization date and the date of first progression while on initial treatment or until death whichever is first, where disease progression will be determined based on RECIST 1.1 criteria. PFS will be estimated using the Kaplan-Meier method and compared between groups using the log-rank test. The median PFS and 95%

confidence interval will be reported. Patients with no defined events observed during the follow-up period will be censored at the last disease assessment date prior to the initiation of sequential treatment, if applicable.

16.322 Second Progression-Free survival (PFS2)

Second progression-free survival (PFS2) is defined as the time interval from re-registration to the sequential treatment phase until the date of progression while on sequential treatment or until death, whichever occurred first. Disease progression will be determined based on RECIST 1.1 criteria. PFS2 will be estimated using the Kaplan-Meier method and compared between groups using the log-rank test. The median PFS2 and 95% confidence interval will be reported. Patients will be censored at the last disease assessment date while on sequential treatment .

16.323 Sequential Treatment Progression-Free Survival (stPFS)

Sequential treatment progression-free survival is defined as the time from randomization until progression while on the sequential treatment or until death, whichever occurred first. Patients who did not experience an event during follow-up will be censored at the last disease assessment date.

Patients who completed initial treatment but did not begin sequential treatment will be censored at the date of last disease evaluation prior to discontinuation of initial treatment. Patients who began sequential treatment but discontinued protocol treatment prior to progression will be censored at the last disease assessment date while on sequential treatment. Analysis methods will mirror those of the other PFS endpoints.

16.324 Objective Response Rate

The objective response rate to initial treatment will be estimated by the number of patients who achieve a best response to initial treatment of complete response or partial response (CR or PR) divided by the total number of evaluable patients. Point estimates and the corresponding 95% confidence intervals for the true success proportions will be calculated.

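### As Section 16.32 is worded, RECIST progression seen after a drug is stopped but before the next therapy is not a PFS event, although Section 11.45 asks sites to document it

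*Combined protocol and SAP*

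**What the plan says.** - **Section 11.45** applies to "Patients with global deterioration of health status requiring discontinuation of treatment without objective evidence of disease progression at that time", where the decline is not due to study treatment or another condition. These patients are to be recorded as PD. The section adds: "Every effort should be made to document the objective progression even after discontinuation of treatment due to symptomatic deterioration".
- **Section 11.0**, which contains 11.45, opens with "Response and progression will be evaluated in this study using the new international criteria" and names RECIST 1.1.
- **Section 16.321 (PFS1)** runs from randomization to "first progression while on initial treatment or until death whichever is first, where disease progression will be determined based on RECIST 1.1 criteria". Patients without an event are censored at their last disease assessment before sequential treatment begins.
- **Section 16.322 (PFS2)** runs from re-registration to RECIST 1.1 progression on sequential treatment, or death. Censoring is at the last assessment on that treatment.
- **Section 16.323 (stPFS)** runs from randomization to progression on sequential treatment, or death, and does not name RECIST. Patients who never start the second treatment are censored at the last evaluation before initial treatment was stopped. Patients who stop the second treatment before progression are censored at the last assessment on it.
- **Sections 8.3 and 8.44** give the radiographic stopping criterion as "Radiographically confirmed disease progression" for regorafenib and "Radiographically confirmed disease progression per RECIST 1.1" for the anti-EGFR antibodies. Both sections also allow stopping for marked worsening of symptoms or physical findings, with radiographic confirmation where possible.
- **Section 18.1** lists a RECIST baseline form for sequential treatment. In event monitoring it collects disease status every 3 months until PD and again at PD.

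**The concern.** Section 11 and Section 16.32 do not join up. Section 11.45 creates a class of PD that needs no objective evidence, and it sends sites to look for objective progression after the drug is stopped. The PFS definitions say nothing about that class, and they tie progression to time on treatment, which excludes scans taken after stopping.

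Two things are at stake. First, two analysts could score the same patient differently and obtain different PFS results from one database. Second, patients who stop because they are declining are likely to progress soon. Censoring them breaks the Kaplan-Meier assumption that censored patients have the same outlook as those still followed. PFS would then look longer than it is.

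**Working it through.** **Does this touch the primary design?** The inputs are in 16.22 and 16.23: 42 deaths, medians of 7.5 and 14.5 months, one-sided 0.1, 1:1 allocation.

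- Hazard ratio: 7.5/14.5 = 0.517.
- Critical hazard ratio: exp(−2 × 1.2816/√42) = 0.673, as stated.
- Power (Schoenfeld): Φ(√42/2 × |ln 0.517| − 1.2816) = Φ(0.855) = 0.804. The plan states 80%, and 79.4% by simulation in 16.24.

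No term depends on how progression is defined, so the OS design stands under any reading. The plan states no power or event target for PFS.

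**One patient followed through the text.** Take a patient who stops the initial drug for deterioration or intolerance without RECIST progression. A scan before the second drug then shows RECIST progression. Section 6.4 allows up to 28 days to re-registration and 7 more to first dose, so the interval can reach 28 + 7 = 35 days. A new baseline for sequential treatment also has to be measured.

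| Reading | PFS1 outcome |
|---|---|
| 11.45 PD counts (deterioration only) | Event; presumably dated at the deterioration, but 16.321 gives no date |
| 16.321 literally, no death observed | Censored at the very scan that shows progression |
| 16.321 literally, later death counted | Event at death, later than the observed progression |
| Treatment taken to mean the treatment phase | Event at the scan |

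Nothing in 16.321 chooses among these.

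For PFS2, a progression scan after the second drug is stopped falls outside the definition. Censoring goes back to the last assessment on the drug, so the scan is not used at all. stPFS has the same rule for those who stop the second drug. For those who never start it, censoring goes back to before the first drug was stopped.

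**Scale, by assumption only.** The documents give no share of progressions that would be lost, so let that share be q. Take 26 evaluable patients per arm (16.22), constant hazards, a PFS1 event in every patient if all progressions count, and no later death rescuing a lost event. With the same q in both arms, events become 52 × (1 − q), and the apparent median is multiplied by about 1/(1 − q):

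| q in both arms | Events of 52 | Median multiplied by |
|---|---|---|
| 5% | 49.4 | 1.05 |
| 10% | 46.8 | 1.11 |
| 20% | 41.6 | 1.25 |

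A simulation with an assumed PFS1 median of 4 months, true hazard ratio 1 and censoring at the last 8-weekly scan left the hazard ratio at about 1.0 in all three rows. It moved only when different shares were imposed by arm. For A/B shares of 10%/5%, 20%/10% and 20%/5% it was about 0.96, 0.90 and 0.87. Nothing in the documents supports any of those pairs. Counting later deaths as events would reduce the loss.

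**The case against.** **The literal reading may not be the intended one.** Section 11.45 sits inside the RECIST section, so RECIST 1.1 in 16.32 could be taken to include it. Being on initial treatment could mean the initial phase, since PFS1 censoring runs to the start of sequential treatment and the initial-treatment RECIST form is also due at end of treatment. These readings are open, but so is the literal one. The text should not leave the choice to the analyst.

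**Death is an event, so many of these patients are not lost.** For PFS1 this largely stands. Censoring applies only to patients with no event, follow-up runs to 3 years, and the assumed OS medians are 7.5 and 14.5 months. But a death in place of an observed progression dates the event too late. In 16.323, moreover, censoring of patients who never start or who stop early is written without an exception for later death.

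**Only secondary endpoints are involved.** This stands and limits the weight of the point.

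**A stronger reading that a reader might infer.** Because only 8.44 names RECIST 1.1 in its radiographic criterion, one might conclude that regorafenib may be stopped on non-RECIST progression while anti-EGFR therapy may not, so that censoring falls mainly in Arm A and PFS1 favours it. The documents do not support this. Both 8.3 and 8.44 allow stopping for symptomatic worsening without radiographic proof, Section 11.0 sets RECIST 1.1 for the whole study, and both arms are planned to receive both regimens. One could also argue that judging whether a decline is treatment-related will differ by drug, because weight loss, fatigue and anorexia are named as regorafenib toxicities in 8.21. But weight loss is listed for irinotecan too (15.47), so the direction cannot be predicted.

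**Conclusion.** The point holds for PFS1, PFS2 and stPFS. On their literal wording, RECIST progression found after a drug is stopped but before the next therapy is not an event at that scan, and the status of symptomatic PD under 11.45 is undefined. The trial collects the information needed to count such progressions and then does not use it, and patients can be censored because they are failing.

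OS, the 42 deaths, the power and the critical hazard ratio of 0.673 are unaffected. The documents give neither the frequency of such patients nor any evidence that it differs by arm. The figures above are therefore illustrations under assumed shares, and no direction or size of bias in the arm comparison can be claimed. The correction is worth making because it is cheap and fixes the result before data are seen.

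**What to change.** 1. In 16.321 to 16.323, replace the on-treatment condition with RECIST 1.1 progression on any scan up to the start of the next anti-cancer therapy, or death. For PFS1 the next therapy is the sequential treatment or any non-protocol therapy, whichever comes first. For PFS2 and stPFS it is the first therapy after the sequential treatment. Name RECIST 1.1 in 16.323 as well.
2. Align the censoring text: the last disease assessment before that next therapy. State whether a death after the next therapy has begun counts, and restate in the same terms the rule for patients who never start sequential treatment.
3. State whether PD due to symptomatic deterioration under 11.45 is an event in the main analysis, and on what date. Run a sensitivity analysis under the other rule. Either choice is defensible: counting it adds subjectivity, and leaving it out risks informative censoring.
4. Separately, reconcile the radiographic progression wording of 8.3 and 8.44.

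The cost is a wording change and one more analysis. Section 18.1 already collects progression documentation and the first non-protocol treatment. The downside is that scans after stopping may not follow the 8-week schedule, so some progression dates will be less regular.

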12.0 Descriptive Factors

- 12.1 ECOG Performance Status: 0 vs. 1 vs. 2
- 12.2 Primary tumor location: cecum vs. ascending vs. hepatic flexure vs. transverse vs. splenic flexure vs. descending vs. sigmoid vs. rectosigmoid vs. rectum. vs other
- 12.3 Microsatellite instability or mismatch repair deficiency tested: yes vs. no.
- 12.31 If yes,
MSI-High (MSI-H/dMMR) vs. MSS/MSI-L/pMMR
- 12.4 ERBB2 (HER2) amplification tested: yes vs. no.
- 12.41 If yes, ERBB2 amplified vs. ERBB2 equivocal vs. ERBB2 not amplified.
- 12.5 BRAF analysis done: yes vs. no.
- 12.51 If yes, wild-type vs. mutated.
12.511 If mutated, V600E mutation: yes vs. no.
- 12.6 KRAS analysis done: yes vs. no.
- 12.61 If yes, wild-type vs. mutated.
- 12.6 NRAS analysis done: yes vs. no.
- 12.61 If yes, wild-type vs. mutated.

13.0 Treatment/Follow-up Decision at Evaluation of Patient

- 13.1 A patient is deemed *ineligible* if after randomization, it is determined that at the time of randomization, the patient did not satisfy each and every eligibility criteria for study entry. The patient may continue treatment off-protocol at the discretion of the physician as long as there are no safety concerns, and the patient was properly registered. The patient will go directly to the event-monitoring phase of the study (or off study, if applicable).
- If the patient received treatment, all data up until the point of confirmation of ineligibility must be submitted. Event monitoring will be required per Section 18.0 of the protocol.
- 13.2 A patient is deemed a *major violation*, if protocol requirements regarding treatment in cycle 1 of the initial therapy are so severely violated that evaluability for the primary endpoint is questionable. All data up until the point of confirmation of a major violation must be submitted. The patient will go directly to the event-monitoring phase of the study. The patient may continue treatment off-protocol at the discretion of the physician as long as there are no safety concerns, and the patient was properly registered. Event monitoring will be required per Section 18.0 of the protocol.
- 13.3 A patient is deemed a *cancel* if he/she is removed from the study for any reason before any study treatment is given. On-study material and the End of Active Treatment/Cancel Notification Form must be submitted. No further data submission is necessary.
- 13.4 Patients who are CR, PR, or SD will continue treatment per protocol with evaluation every 8 weeks, until disease progression or intolerance.
- 13.5 Patients who develop PD while receiving therapy on the initial treatment may be re-registered to the sequential treatment phase, or may go to event-monitoring, per physician discretion. If a patient develops PD while receiving sequential treatment, they will be followed for survival (i.e. event monitoring phase) every 3 months (± 7 days) for 3 years after randomization (per Section 18.0).
- 13.6 Patients who go off protocol treatment on the initial treatment for reasons other than PD may be re-registered to the sequential treatment phase, or may go to event-monitoring, per physician discretion. If a patient goes off protocol treatment while receiving sequential treatment, they will be followed for survival (i.e. event monitoring phase) every 3 months (± 7 days) for 3 years after randomization (per Section 18.0).
- 13.7 Patients have the option to complete cfDNA testing at study completion and are encouraged to register with protocol ACCRU-GI-1611 (COLOMATE). The results of the cfDNA test will be used in protocol ACCRU-GI-1611 (COLOMATE) to identify genomic alterations and facilitate enrollment on COLOMATE companion clinical trials. Sites will access results by creating an account at [REDACTED] Sites will be notified by Guardant Health via email when results are available in the portal. See detailed instructions on the ACCRU website under Manuals and Forms.

